# **3.4. EXPLORATORY ENDPOINTS**

- The primary endpoints identified above will be repeated in the following 3 age groups: 4 to 11 years, 12 to 17 years, and 4 to 55 years, inclusive
- The first 3 key secondary endpoints will be repeated in the following 4 age groups: 4 to 11 years, 12 to 17 years, 18 to 55 years, and 4 to 55 years, inclusive
- Treatment satisfaction assessment using the Treatment Satisfaction Questionnaire for Medication (TSQM-9) and an exit survey with palatability questions

### 4. ANALYSIS POPULATIONS

The following analysis populations will be defined for this study.

# 4.1. SAFETY POPULATION

The Safety population will consist of all subjects who receive at least one dose of randomized study treatment (i.e., not including food product administered during DBPCFC). The Safety population will be used for summaries of safety parameters. Subjects will be analyzed according to treatment received.

# 4.2. INTENT-TO-TREAT (ITT) POPULATION

The ITT population (i.e., the Full Analysis Set) will consist of all randomized subjects who received at least one dose of randomized study treatment. Subjects will be analyzed according to randomized treatment. The ITT population will be used as the primary analysis population for all analyses of efficacy endpoints. If no subjects received the incorrect treatment, the ITT population will be the same as the safety population.

Since only four subjects were randomized but not treated and due to the double blind nature of the trial, no bias is introduced by excluding these four subjects from the ITT population.

# 4.3. COMPLETER POPULATION

The Completer population includes all subjects in the ITT population who complete treatment and have an evaluable Exit DBPCFC, where an evaluable Exit DBPCFC is defined as completion of at least the peanut part of the food challenge. Sensitivity analyses and supportive analyses of the primary endpoint, and key secondary endpoints, and other secondary endpoints will be performed using the Completer population. These supportive analyses are considered important because they will provide the basis for informing patients and their families of their chances of achieving a clinically relevant level of desensitization if Up-dosing and maintenance therapy are achieved.

# 4.4. PER PROTOCOL (PP) POPULATION

The Per Protocol (PP) population will be a subset of the Completer population, limited to subjects who have no major protocol deviations that may influence the desensitization response. Additional criteria to exclude subjects from the PP population may be added. Any changes will be documented in a SAP amendment or other supporting document. Exclusions will be determined by blinded review before database lock and overall study unblinding. Subjects will be analyzed according to randomized treatment. The PP

population differs from the Completer population only in that it excludes subjects who may have undergone the Exit DBPCFC despite having major protocol deviations.

Analyses of the primary and all secondary efficacy endpoints will be performed on the PP population if the PP population differs from Completer population by >5% in either treatment arm. Sensitivity analyses of selected endpoints may, however, be performed if the PP population differs from the Completer population by  $\leq$ 5% in both treatment arms.

The decision to conduct the optional analyses in the PP population will be made before database lock and overall study unblinding.

### 5. **PROTOCOL DEVIATIONS**

A Protocol Violation (i.e., major protocol deviation) is a deviation from the Institutional Review Board (IRB) approved protocol that may affect the subject's rights, safety, or wellbeing and/or the completeness, accuracy and reliability of the study data. In addition, protocol violations include willful or knowing breaches of human subject protection regulations, or policies, any action that is inconsistent with medical, and ethical principles, and a serious or continuing noncompliance with federal, state, local or institutional human subject protection regulations, policies, or procedures.

A non-major protocol deviation is any change, divergence, or departure from the study design or procedures of a research protocol that does not have a major impact on the subject's rights, safety or well-being, or the completeness, accuracy and reliability of the study data.

All protocol deviations will be reported in the data system on a specific case report form (CRF):

- Inclusion Criteria
- Exclusion Criteria
- Received incorrect study treatment
- Randomization issue/ randomized to wrong stratum
- ICF
- SAE Not Reported
- Visit Out of Window
- Missed Study Visit
- Procedure Not Per Protocol
- Prohibited Concominant Medication
- Lab Sample missed
- Study Drug Compliance
- Other (with free text field to record details)

These protocol deviations will be reviewed in a blinded fashion prior to database lock and their categorization as major or minor will be determined prior to database lock and will be used to help determine the PP population. All protocol deviations, both major and non-major, will be listed and included in the study report.

#### 6. GENERAL ASPECTS FOR STATISTICAL ANALYSIS

# 6.1. STRATA AND COVARIATES

The primary efficacy endpoint of desensitization response rates in pediatric subjects will compare treatment groups based on Farrington-Manning confidence interval for the difference in binomial proportions without stratification.

The key secondary endpoint of maximum severity of symptoms in pediatric subjects at any challenge dose of peanut protein during the Exit DBPCFC will include a stratification factor for region (North America or Europe). Other secondary efficacy endpoints may include a stratification factor for region and/or a covariate for the corresponding baseline value, where appropriate.

Exploratory analyses of the primary efficacy endpoint and key secondary endpoints may be performed where specified baseline factors (see Section 9.6.3) are included as stratification factors in the analyses to explore their effects on study endpoints.

#### 6.2. SUBGROUP ANALYSES

The primary analysis of efficacy and safety data will be performed in pediatric subjects ages 4-17. Additional analysis will be performed using the following subgroups of age, geographic region, or both age and geographic region.

Age Group:

- Ages 4-11 Years
- Ages 12-17 Years
- Ages 18-55 Years
- Ages 4-55 Years

Geographic Region:

- North America (NA)
- Europe (EU)

For countries with at least 3 subjects in each treatment arm, subgroup analyses may be performed by country.

In select analyses, age group and/or region will be included as factor(s) in the statistical analyses. When any region has fewer than 3 subjects with an evaluable response for the variable of interest in either treatment arm, region will be excluded from the model.

In addition to subgroup analyses described above, additional population subsets may be defined and utilized for select analyses. These subsets will include the following:

Baseline ps-IgE:

- $< 100 \text{kU/L} \text{ versus} \ge 100 \text{kU/L}$
- Cutoff predictive of screening MTD ≤30 mg (as determined from the Screened Population, see Section 9.6.6.)

Baseline SPT wheal diameter:

- < 8mm versus  $\ge 8$ mm
- Cutoff predictive of screening MTD ≤30 mg (as determined from the Screened Population, see Section 9.6.6)

Additional subgroups for ps-IgE and SPT wheal diameter may be defined (e.g., those predictive of subjects who fail to reach the target dose of 300 mg, see Section 9.6.7) and evaluated in exploratory analyses. These will be described as such in the study report.

Other subgroups:

- Asthmatic subjects
- Subjects enrolled in protocol ARC004

# 6.3. MULTIPLE COMPARISONS AND MULTIPLICITY

The key secondary endpoints and other secondary efficacy endpoints will be tested in a hierarchical method, as described in Sections 9.3 and 9.5.

No other adjustments will be made for multiple comparisons.

#### 6.4. SIGNIFICANCE LEVEL

Unless stated otherwise, all statistical tests will be two-sided, with a significance level of 0.05. Confidence intervals (CIs) will be calculated at the 95% level, reflecting a type I error rate of 0.05.

# 6.5. STATISTICAL NOTATION AND METHODOLOGY

Unless stated otherwise, the term "descriptive statistics" refers to the number of subjects (n), mean, median, standard deviation, minimum, and maximum for continuous variables and frequencies and percentages for categorical variables.

Unless specified otherwise, the denominator for percentages for categorical data will be based on the number of subjects or observations with non-missing data appropriate for

summary purposes. The denominator for percentages for incidence data (such as adverse events) will be based on the number of subjects in the analysis population "at risk".

Minimum and maximum values will be presented at the precision of the original value, means, medians will be rounded to 1 decimal place greater than the precision of the original value, standard deviations and standard errors will be rounded to 2 decimal places greater than the precision of the original value. Percentages will be rounded to 1 decimal place. Percentages that round down to 0 or up to 100% will be displayed as "<0.1%" and ">99.9%", respectively.

All summary tables will be presented by treatment group displayed as AR101 and Placebo. For disposition, demographic, and other summaries of baseline and history data, a Total column for both treatment groups combined will be included.

All relevant data collected in the database will be included in data listings and sorted by stratified age group, treatment group, subject number, test/measurement, and visit and time point as appropriate. The treatment group will be displayed in the same order as appeared in the summary tables.

Any change to the data analysis methods described in the protocol or SAP will require an amendment if it changes a principal feature of the protocol or SAP. Any other change to the data analysis methods described in the protocol or SAP, and the justification for making the change will be described in the clinical study report and where appropriate in a Note to File or amendment to the SAP before database lock. Additional exploratory analyses of the data will be conducted as deemed appropriate.

# 7. DATA HANDLING METHODS

# 7.1. VISIT WINDOWS

All information will be listed, summarized, and analyzed according to the nominal visit time point, study period, or dose. No visit windowing will be performed.

#### 7.2. DATA PRESENTATION

Individual subject data listings will be provided to support summary tables and serve as a data source. Unless otherwise noted, all data collected during the study for all randomized subjects will be included in data listings. Listings will be sorted by age group (ages 4-17, ages 18-55), treatment group, subject identifier, and visit date or time point (where applicable). If a listing includes screen failures, they will be listed as treatment group 'NONE' and sorted after all randomized subjects.

Unscheduled visits will be listed but not included in by-visit summaries. Results from unscheduled visits may be used as baseline values, and for other derivations not tied to visit names (for example, unscheduled visits are included in the determination of worst post-baseline values for physical examination results).

#### 7.3. MAXIMUM TOLERATED DOSE AT DBPCFC

The MTD for a DBPCFC is defined as the maximum single dose of peanut protein resulting in no more than mild symptoms and assessed by the investigator to have been tolerated (i.e., subject did not experience any dose-limiting symptoms). Any symptom requiring treatment is inherently dose-limiting; thus, a dose during a DBPCFC cannot be considered "tolerated" if treatment was deemed necessary by the investigator. The MTD at the Screening DBPCFC will be used as the baseline amount of peanut protein tolerated. If a subject is administered non-standard doses at a DBPCFC, the MTD will be considered as the highest standard dose (whether administered or not) less than the highest tolerated nonstandard dose.

When describing the MTD at the Exit DBPCFC, in terms of the cumulative amount of peanut protein, the 1 mg dose will not be included. Thus subjects who tolerate all dose levels from 3 mg to 300 mg or 1 mg to 300 mg have a cumulative MTD of 443 mg.

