6.6.2 Exit Double-Blind, Placebo Controlled Food Challenge (DBPCFC)

The Exit DBPCFC will be conducted in a manner similar to the Screening DBPCFC, but starting at a dose of 3 mg of peanut protein (except for subjects who failed their Screening DBPCFC at 1 mg), and with the last 3 challenge doses progressing from 300 mg (443 mg cumulative) to 600 mg (1043 mg cumulative) and then to 1000 mg (2043 mg cumulative) of peanut protein as shown in **Table 6-1**.

The same vehicle food should be used for the Exit DBPCFC as was used for the Screening DBPCFC.

Dosing with study product should continue on the days between the two parts of the Exit DBPCFC, according to the same dosing guidelines that apply throughout the Maintenance Period.

Subjects who failed their Screening DBPCFC at the 1 mg challenge dose of peanut protein will be required to start the Exit DBPCFC with a 1 mg dose. At the investigator's discretion, a 1 mg dose may be added at the beginning of the escalation (for a maximum cumulative dose of 2044 mg peanut protein) of any subject's Exit DBPCFC.

Subjects will be considered desensitization responders for the primary endpoint analysis for North America or Europe if they are able to tolerate an Exit DBPCFC challenge dose of 600 mg (1043 mg cumulative) or 1000 mg (2043 cumulative) of peanut protein with no, or only mild, symptoms, respectively.

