### 7.4. CLASSIFICATION OF RESPONDER STATUS

#### 7.4.1. Classification as a responder

To be a 600 mg responder, a subject must meet both of the following conditions:

- 1) Must have attained a maximum tolerated single dose (MTD) ≥600 mg of peanut protein on Exit DBPCFC
- 2) Must not have experienced more than mild symptoms through 600 mg of peanut protein on Exit DBPCFC.

Classification as a 300 mg responder and a 1000 mg responder are defined similarly.

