#### 7.4.2. Classification as a non-responder

If a subject cannot be classified as a responder, then that subject should be classified as a non-responder. If a subject meets any of the following conditions, then the subject is a non-responder:

- 1) Discontinued before the Exit DBPCFC or did not undergo an Exit DBPCFC for any other reason
- 2) Failed the Exit DBPCFC (e.g., a subject who did not tolerate a single dose of at least 600 mg of peanut protein with at most mild symptoms is a 600 mg non-responder).

Classification as a 300 mg non-responder and a 1000 mg non-responder are defined similarly.

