#### 9.3.2. Maximum Severity of Symptoms

The objective of analyzing this key secondary efficacy endpoint is to determine if pediatric subjects from the AR101 group will have less chance of developing more severe levels of symptom severity compared to pediatric subjects from the placebo group. Symptom severity will be determined at 4 levels: 0-None, 1-Mild, 2-Moderate, 3-Severe or higher (severe, life threatening, fatal). Subjects who experience no symptoms will be assigned a severity of 0-None. Symptom severity data will be collected at each challenge dose of peanut protein during the Exit DBPCFC (3 mg, 10 mg, 30 mg, 100 mg, 300 mg, 600 mg, and 1000 mg). The analysis of this key secondary endpoint will be conducted in the pediatric subject subset of the ITT population.

The maximum severity of symptoms observed in the DBPCFC at any dose (1000 mg or lower) will be used for each subject in the primary analysis of this key secondary endpoint.

The number and percent of subjects by maximum severity at the Exit DBPCFC will be tabulated by treatment arm. The Cochran-Mantel-Haenszel statistic (with equally spaced scores) will be used to test for a treatment difference. The test will be stratified by Region. The mean of the numerical values assigned to maximum severity by treatment group will also be reported.

The primary analysis of this key secondary endpoint will test the following hypotheses:

- H0: The maximum severity of symptoms at the Exit DBPCFC at any dose is the same for the AR101 and placebo treatment arms in all strata.
- HA: The maximum severity of symptoms at the Exit DBPCFC at any dose is different between the AR101 and placebo treatment arms in at least one stratum.

For the primary analysis of this key secondary endpoint, subjects without an Exit DBPCFC will be assigned their maximum severity during the Screening DBPCFC, which equates to no change from screening.

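### Read literally, the SAP 7.3 rule for non-standard challenge doses ignores standard doses tolerated later and can turn a true responder into a non-responder

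*SAP*

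**What the plan says.** SAP 7.3 opens with a general definition: "The MTD for a DBPCFC is defined as the maximum single dose of peanut protein resulting in no more than mild symptoms", with the added condition that the investigator judged the dose tolerated. A special case follows. It begins "If a subject is administered non-standard doses at a DBPCFC" and continues that "the MTD will be considered as the highest standard dose (whether administered or not) less than the highest tolerated nonstandard dose". Nothing limits the special case to a non-standard dose that was the last or the highest one tolerated.

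SAP 9.3.2 lists the standard Exit doses as "3 mg, 10 mg, 30 mg, 100 mg, 300 mg, 600 mg, and 1000 mg"; a 1 mg dose is required for some subjects and optional for others.

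The derived MTD feeds responder status. The first condition for a 600 mg responder in SAP 7.4.1 is "Must have attained a maximum tolerated single dose (MTD) ≥600 mg of peanut protein on Exit DBPCFC", and the 300 mg and 1000 mg responders are defined in the same way. SAP 7.4.2 adds: "If a subject cannot be classified as a responder, then that subject should be classified as a non-responder".

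Two other places go by the dose actually tolerated. The example in SAP 7.4.2 describes a 600 mg non-responder as "a subject who did not tolerate a single dose of at least 600 mg of peanut protein". Protocol 6.6.2 counts subjects as responders "if they are able to tolerate an Exit DBPCFC challenge dose of 600 mg (1043 mg cumulative) or 1000 mg" with no or only mild symptoms.

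**The concern.** A rule for non-standard amounts is needed, because a tolerated 700 mg or 900 mg has to be placed on the standard scale. As worded, however, the rule also covers a child with one wrong amount at an early step who then completes the standard sequence. For that child the highest tolerated non-standard dose is a small number that says nothing about the top dose tolerated.

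The derived MTD is a required condition for the North America and Europe primary endpoints and for the key secondary response rates. It is also the outcome in the discrete hazards model (SAP 9.5.1) and the change-from-baseline ANCOVA (SAP 9.5.2). The sentence applies to any DBPCFC, so it reaches the Screening MTD too. That value is the covariate in both models and, under SAP 7.4.3, the value imputed for subjects without an Exit challenge.

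**Working it through.** **1. Apply the rule as written.** Take a child who tolerates every dose given at Exit with no more than mild symptoms, with one step replaced by a non-standard amount.

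| Amount given in place of standard step | Literal MTD (mg) | Literal status at 300 / 600 / 1000 mg | Highest standard dose not above the highest dose tolerated (mg) |
|---|---|---|---|
| 5 for 3 mg | 3 | no / no / no | 1000 |
| 20 for 10 mg | 10 | no / no / no | 1000 |
| 60 for 30 mg | 30 | no / no / no | 1000 |
| 200 for 100 mg | 100 | no / no / no | 1000 |
| 250 for 300 mg | 100 | no / no / no | 1000 |
| 500 for 600 mg | 300 | yes / no / no | 1000 |
| 700 for 600 mg | 600 | yes / yes / no | 1000 |
| 900 for 1000 mg | 600 | yes / yes / no | 600 |
| 2000 for 1000 mg | 1000 | yes / yes / yes | 1000 |

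The last two rows are the cases the sentence handles well, where the non-standard dose is the top dose. In general, 600 mg response is lost when the highest tolerated non-standard dose is below 600 mg, and 1000 mg response when it is below 1000 mg. For the 20-for-10 child, log10 MTD falls from 3.0 to 1.0.

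**2. Screening.** Suppose a child is given 5 mg for 3 mg, tolerates 10 and 30 mg, and reacts at 100 mg. The general definition gives a baseline of 30 mg and the literal sentence gives 3 mg. If the Exit MTD is correct, the change from baseline rises by log10(30/3) = 1.0.

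**3. Reproduce the plan's power.** Inputs, from protocol 9.4:
- 495 children at 3:1, taken as 371 AR101 and 124 placebo
- North America: 50% v 20%, margin 0.15
- Europe: 30% v 15%, margin 0
- two-sided 0.05

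Power = Φ[(p1 − p2 − margin − 1.96·s0)/s1]. Here s1 uses the assumed rates, and s0 uses the Farrington-Manning restricted estimates under the null.

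- North America: restricted rates 0.458 and 0.308; s0 = √(0.458·0.542/371 + 0.308·0.692/124) = 0.0489; s1 = √(0.25/371 + 0.16/124) = 0.0443. Then (0.15 − 1.96·0.04887)/0.04432 = 1.22, so power is 88.9%. The plan states approximately 89%.
- Europe: s0 = 0.0456, s1 = 0.0399; (0.15 − 1.96·0.04564)/0.03993 = 1.52, so power is 93.5%. The plan states at least 93%.

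**4. Size of the effect.** One lost AR101 responder costs 1/371 = 0.27 points. The documents give no frequency of non-standard doses. As an assumption, let a share e of responders in both arms lose that status, so each rate is multiplied by (1 − e).

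| e | AR101 v placebo (North America) | Difference | AR101 responders lost, 371·0.5·e | Placebo responders lost, 124·0.2·e | Power, North America | Power, Europe |
|---|---|---|---|---|---|---|
| 0 | 50.0% v 20.0% | 30.0 | 0 | 0 | 88.9% | 93.5% |
| 0.5% | 49.75% v 19.9% | 29.85 | 0.9 | 0.1 | 88.4% | 93.4% |
| 1% | 49.5% v 19.8% | 29.7 | 1.9 | 0.2 | 87.8% | 93.2% |
| 2% | 49.0% v 19.6% | 29.4 | 3.7 | 0.5 | 86.6% | 92.9% |
| 5% | 47.5% v 19.0% | 28.5 | 9.3 | 1.2 | 82.4% | 91.8% |

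**The case against.** The strongest reply is that the sentence is loosely worded and has a natural reading. SAP 7.3 first defines the MTD as the maximum tolerated single dose, and a child who tolerates a standard 1000 mg meets that definition. The parenthesis about doses not administered suggests that the special case was meant only to place a non-standard top dose on the standard scale. That is probably the intent, but the sentence does not say so. A specific rule normally displaces a general one when it is programmed.

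There are partial safeguards. Protocol 6.6.1 and SAP 2.7 require an unaltered dose sequence, so a non-standard amount is a departure from protocol. SAP section 11 has desensitization status queried before each subject is unblinded and classified by blinded staff before lock. A child recorded as tolerating 1000 mg with a derived MTD of 10 mg might be noticed. However, that review classifies by SAP 7.4, which uses the derived MTD, and it states no override.

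Two stronger readings are tempting and should not be drawn:

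- A reader might infer that the rule yields no MTD when the only non-standard dose was not tolerated, such as 700 mg after 300 mg was tolerated. In that case the special sentence has no tolerated non-standard dose to act on. The general definition still applies and gives 300 mg.
- A reader might infer a material bias in the primary result. The documents give no frequency of such doses, so this is unsupported. For response rates the error mainly removes true responders, more of them in the AR101 arm in absolute terms, and so works against AR101. At Screening, affected subjects can move the other way on change from baseline, but only those subjects, and only within a challenge capped at 100 mg.

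**Conclusion.** The point holds as a wording error in a derivation rule. The rule gives a wrong result when followed literally, contradicts the first sentence of its own section and protocol 6.6.2, and reaches the primary endpoint through SAP 7.4.1. The classification result follows from the text alone.

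The numerical size rests on assumptions: 371 and 124 children, the plan's response rates, and an assumed 0.5% to 5% of responders in both arms losing that status. On those terms North America power is 88.4% to 82.4% instead of 88.9%, and Europe power is 93.4% to 91.8% instead of 93.5%. If errors are rare the effect is small. The case for correcting the rule is that responder status should not depend on how a programmer resolves an ambiguous sentence.

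**What to change.** Keep the first sentence of SAP 7.3 as the definition of the MTD. Replace the special sentence with wording such as:

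*If the highest dose tolerated with no more than mild symptoms is itself a non-standard dose, the MTD is the next standard dose below it, whether or not that dose was given. Otherwise the MTD is the highest standard dose tolerated with no more than mild symptoms, regardless of any non-standard dose given at another step.*

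State that this applies at both Screening and Exit. The symptom condition has to stay in the text. Protocol 6.6 and 6.7.2 allow a dose with moderate symptoms to be assessed as tolerated on rare occasions, so wording based on tolerance alone could raise the MTD for such children.

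The cost is one SAP sentence and a small change to the derivation program. SAP 6.5 provides the route, by amendment or note to file before database lock. No data collection changes.
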